**Table 2-1 Analysis visit windows (except for Lab and ECG)**

Study visit	Target day (time)	Study day window
Baseline	1 (-1h)	Day -28 to Day 1 predose
Day 1	1	1
24 hours	2	2
Day 8	8	3 - 11
Day 15	15	12 - 18
Day 22	22	19 - 25
Day 29	29	26 - EOS

Laboratory assessments are only measured on Baseline, 24 hours post-dose on Day 2 and Day 29 (EOS), the visit window is listed in [Table 2-2](#). ECG assessments are measured similarly as Lab with additional measures on Day 1(0.5h, 1.5h and 4h post-dose), the visit window is listed in [Table 2-3](#).

**Table 2-2 Analysis visit windows for Laboratory**

Study visit	Target day (time)	Study day window
Baseline	1 (-1 h)	Day -28 to Day 1 pre-dose
24 hours	2	Day 1 post-dose to Day 4
Day 29	29	5 - EOS

**Table 2-3 Analysis visit windows for ECG**

Study visit	Target day (time)	Study day window
Baseline	1 (-1 h)	Day -28 to Day 1 pre-dose
Day 1	1 (0.5 h, 1.5 h, 4 h)	Day 1 post-dose to end of Day 1
24 hours	2	Day 2 to Day 4
Day 29	29	5 - EOS

## **2.3 Other antidepressants or any combinations Patient disposition, demographics and other baseline characteristics**

### **2.3.1 Patient disposition**

Participants' disposition will be assessed at screening and at the end of study.

The number of participants screened and rescreened will be reported. Subject dispositions at the end of screening phase will be summarized. The primary reason for not completing the screening phase will also be summarized.

Information on inclusion and exclusion criteria will be provided for subset of screened patients not continuing to randomization.

The number and percentage of participants who completed study will be summarized based on FAS. For early study discontinuations, the reasons will be summarized.

The details of the screening and study dispositions will be listed at subject level.

The number of patients randomized will be summarized by country.

For protocol deviation (PD), the number and percentage of participants will be provided by PD category and deviation term and summarized for each arm. All PDs will be listed by treatment arms and by PD categories.

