1.1.3 MIJ821 Clinical summary

The MIJ821 clinical development program aims to evaluate MIJ821 as a short-term, fast-acting treatment for adult participants with MDD who have acute suicidal ideation and behavior (initial indication) and as a treatment of adult participants with TRD (follow-on indication).

MIJ821 has been studied in a Phase 1 First-In-Human study (FIH, CMIJ821X2101) in healthy volunteers (HV) and in a Phase 2a Proof-of-Concept (PoC CMIJ821X2201) clinical study in participants with TRD after i.v. administration. A Phase 1 study is also ongoing to investigate the safety, tolerability and pharmacokinetic (PK) of subcutaneous MIJ821 in HVs (CMIJ821A02101).

First-In-Human study (CMIJ821X2101)

In a FIH study, MIJ821 was intravenously administered at single ascending doses (SAD) of 0.016, 0.048, 0.16, 0.24, 0.32, and 0.48 mg/kg (Part 1) and at repeated doses of 0.32 mg/kg given one week apart (Part 2) to HVs. Dissociative AEs, amnesia and sedation were observed at doses higher than 0.16 mg/kg.

In term of pharmacokinetics, no obvious PK difference has been identified between the two dosing events in the repeated dose part of the study.

PoC study in TRD participants (CMIJ821X2201)

This PoC study evaluated the safety and efficacy responses to MIJ821 in participants suffering from TRD (defined as failing two or more prior antidepressants, one in the current episode) assessed by the MADRS, a validated and widely employed method in depression trials (see details in Section 8.3.1). Participants were randomized with a ratio of 3:3:3:3:6:4 to one of six treatment arms: i) MIJ821 0.16 mg/kg one infusion per week (weekly), ii) MIJ821 0.16 mg/kg one infusion every other week (biweekly), iii) MIJ821 0.32 mg/kg weekly, iv) MIJ821 0.32 mg/kg biweekly, v) placebo weekly, and vi) ketamine 0.5 mg/kg weekly.

A total of 72 participants were randomized: 41 on MIJ821 across the 4 MIJ821 arms, 11 on ketamine and 20 on placebo. Out of these 72 participants randomized, 70 received study drug and were included in both efficacy and safety analyses. Two participants were randomized but did not receive study drug: 1 patient in MIJ821 0.32 mg/kg biweekly arm for physician decision and 1 patient in ketamine arm for adverse event before treatment. Overall, 53 (75.7%) completed the treatment and 50 (71.4%) completed the follow-up period. The most common reason for treatment discontinuation was participant/guardian decision (15.7%).

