8.1.2 Information to be collected on screening failures

Participants who sign an ICF and subsequently found to be ineligible prior to randomization will be considered a screen failure. The reason for screen failure should be recorded on the appropriate CRF. The demographic information, informed consent, and the Inclusion/Exclusion pages must also be completed for screen failure participants. No other data will be entered into the clinical database for participants who are screen failures, unless the participant experienced a SAE during screening phase (see SAE Section 10.1.3 for reporting details). If the participant fails to be randomized, the IRT must be notified within 2 days of the screen fail that the participant was not randomized.

Participants who are randomized and fail to start treatment, e.g. participants randomized in error will be considered an early terminator. The reason for early termination should be recorded on the appropriate CRF.

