12.1 Analysis sets

The Full Analysis Set (FAS) comprises all randomized participants who received a dose of the randomized treatment. Participants will be analyzed according to the study treatment received.

The Safety Set includes all participants who received any study drug. Participants will be analyzed according to the study treatment received.

The PK analysis set will include all participants with at least one available valid (i.e. not flagged for exclusion) PK concentration measurement, who received any study drug and with no protocol deviations that impact on PK data.

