## 5.5 Rule of exclusion criteria of analysis sets

**Table 5-5** Participants classification

Analysis Set	Criteria that cause subjects to be excluded
FAS	Not randomized Mistakenly randomized and no double-blind study drug taken
SAF	No double-blind study drug taken

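### Study completion is summarised on the FAS, which leaves out at least those randomised in error and never dosed, although the protocol counts them as early terminators; any such case raises the reported completion percentage.

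*SAP*

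**What the plan says.** **Disposition.** On study completion, SAP 2.3.1 reads: "The number and percentage of participants who completed study will be summarized based on FAS". The next sentence is "For early study discontinuations, the reasons will be summarized"; it names no analysis set, but its position suggests that the FAS carries over. The same section then adds: "The details of the screening and study dispositions will be listed at subject level". That listing is not tied to the FAS.

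**Status of undosed participants.** Protocol 8.1.2 covers participants who are randomised but do not start treatment. Its example is that "participants randomized in error will be considered an early terminator", and the site must enter the reason on the CRF.

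**FAS in the protocol.** Section 12.1 limits it to "all randomized participants who received a dose of the randomized treatment".

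**FAS in the SAP.** Apart from people who were never randomised, Table 5-5 in section 5.5 excludes only those who meet this condition: "Mistakenly randomized and no double-blind study drug taken".

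**Other sets in use.** SAP 2.3.2 summarises demographics and baseline characteristics on the Randomized set. Protocol 12.3 places discontinuation reasons on the Safety Set. SAP section 4 reports no change to the protocol's analyses.

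**The concern.** A disposition table should account for everyone who was randomised. Here its denominator can leave out people whom the protocol itself classes as having ended the study early. They are by definition non-completers, so removing them can only raise the completion percentage.

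Three things are at stake, all in descriptive reporting:

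- With 14 per arm, one missing participant visibly changes an arm's completion rate.
- The reasons for loss between randomisation and dosing are collected but may not reach the summary table.
- The baseline tables (Randomized set) and the disposition table (FAS) can have different totals, with no table explaining the gap.

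The SAP does expect such cases: section 2.1.1.2 gives a Day 1 rule for participants who are randomised and not dosed.

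**Working it through.** **Step 1. Who is in the denominator.** Setting protocol 8.1.2 and 12.1 beside SAP Table 5-5:

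| Participant | Status under protocol 8.1.2 | FAS, protocol 12.1 | FAS, SAP Table 5-5 |
|---|---|---|---|
| Randomised in error, not dosed | Early terminator | Out | Out |
| Correctly randomised, not dosed | Early terminator | Out | In |
| Correctly randomised, given the assigned treatment | Not covered by this rule | In | In |

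The first row is lost under both definitions. The second depends on which definition is applied. The text of SAP 2.2 is not available in the public copy, so it cannot settle this.

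**Step 2. The proof-of-concept figures in protocol 1.1.3.** Of 72 randomised, 70 were dosed, 53 completed treatment and 50 completed follow-up. The reported percentages use the dosed base:

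- Treatment: 53/70 = 75.7%, as reported. On those randomised, 53/72 = 73.6%, which is 2.1 points lower.
- Follow-up: 50/70 = 71.4%, as reported. On those randomised, 50/72 = 69.4%, which is 2.0 points lower.

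**Step 3. Size in this trial.** Let N be the number randomised, k the number excluded from the FAS and c the number completing. The overstatement is c/(N − k) − c/N. The documents do not give k or c, so the values below are assumptions. With N = 56 and completion near 90%:

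| k | On the FAS | On those randomised | Difference |
|---|---|---|---|
| 0 | 50/56 = 89.3% | 50/56 = 89.3% | 0 |
| 1 | 50/55 = 90.9% | 50/56 = 89.3% | 1.6 points |
| 2 | 49/54 = 90.7% | 49/56 = 87.5% | 3.2 points |
| 4 | 47/52 = 90.4% | 47/56 = 83.9% | 6.5 points |

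For k = 1 the difference runs from 1.3 points (39/55 against 39/56) to 1.8 points (55/55 against 55/56) as completion goes from about 70% to 100%.

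In one arm of 14 with one excluded participant, 12/13 = 92.3% against 12/14 = 85.7%, a difference of 6.6 points. The range is 4.9 points (9/13 against 9/14) to 7.1 points (13/13 against 13/14).

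**Step 4. How likely it is.** Assume the proof-of-concept rate of undosed participants, 2/72 = 2.8%, and the protocol's FAS:

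- Expected number among 56: 56 × 2/72 = 1.56.
- Chance of at least one: 1 − (70/72)^56 = 0.79.

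These two figures do not carry over to Table 5-5. Protocol 1.1.3 reports that "Two participants were randomized but did not receive study drug", one because of a physician decision and one because of an adverse event before treatment. Neither is described as randomised in error, so on the stated reasons Table 5-5 would keep both. The documents give no rate for the narrower group.

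**The case against.** The strongest objection is that the completion sentence stands in the SAP, and the only SAP rule on FAS membership that can be read is Table 5-5. A correctly randomised participant who is not dosed stays in under that rule. A reader might infer from 2.3.1 that the FAS removes every undosed participant. That follows from protocol 12.1 but not from Table 5-5, and the documents do not show which governs. This part of the objection stands. It limits the 1.56 and the 79% to the protocol definition, along with the example of loss to an adverse event before dosing.

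A reader might also infer that the reasons for leaving are omitted from reporting. The documents do not support that: the sentence on reasons names no set, and the subject-level listing is not restricted to the FAS. At worst the reasons are missing from the summary.

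Two further points have weight. Protocol 12.3 already put discontinuation reasons on the Safety Set, which also contains only dosed participants, so the gap did not begin with the SAP. And since the baseline tables give the number randomised per arm, a careful reader could work out the shortfall by subtraction.

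None of this supports the FAS as the base for completion. Those randomised in error and not dosed are excluded under either definition, and neither document gives a reason for counting completion without them.

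**Conclusion.** The point holds as a minor, conditional reporting bias. The direction is certain: any early terminator outside the FAS raises the completion percentage. The size is about 1.6 points overall (range 1.3 to 1.8) and about 6.6 points in that person's arm (range 4.9 to 7.1) for each excluded participant, assuming 56 randomised, 14 per arm and completion between about 70% and 100%.

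Whether it occurs is not certain. With no excluded participant the effect is zero. The same is true if the only undosed participants were correctly randomised and Table 5-5 governs. It would therefore go too far to say that the plan will overstate completion.

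The primary test and the power are not touched by the choice of disposition denominator.

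**What to change.** 1. In SAP 2.3.1, base both study completion and discontinuation reasons on the Randomized set by randomised arm, and name the set in both sentences.
2. Add a row to that table for participants randomised but not dosed, with their reasons.
3. Make the FAS definition the same in protocol 12.1 and SAP Table 5-5, or state in the SAP which one applies.
4. Record in SAP section 4 that the set for discontinuation reasons differs from the Safety Set named in protocol 12.3.

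The cost is a line in 2.3.1, a table row and short wording changes. The Randomized set is already in use in SAP 2.3.2, and protocol 8.1.2 already has the reasons collected, so no new data are needed. Items 1 and 2 work however the FAS conflict is resolved.

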### **2.3.2 Demographics and other baseline characteristics**

Demographic variables and other baseline characteristics will be summarized for each randomized treatment arm and for all participants (total) based on Randomized set.

Participant demographic and baseline characteristics will include:

- Age
- Sex
- Ethnicity
- Race
- Height
- Weight
- BMI and BMI group (<25; >=25 and <30; >=30)
- Employment status
- Social status
- Region (USA, Europe, Japan)

Disease characteristics at baseline will include:

- Drug class of baseline antidepressants: Selective Serotonin-Reuptake Inhibitors (SSRIs); Serotonin-Norepinephrine Reuptake Inhibitors (SNRIs); Other antidepressants or any combinations

- Baseline SoC category: Antidepressant in monotherapy; Antidepressants in combinations; Antidepressants + Augmentation
- CYP2D6 metabolizer phenotypes classifications (Ultrarapid metabolizers, Normal metabolizers, Intermediate metabolizers, Poor metabolizers)
- Baseline MADRS score and category (<30, 30-34, 35-40, >40)
- Disease duration (years) derived as (randomized date – Date MDD first ever diagnosed) / 365.25
- Duration of current depressive episode (weeks) derived as (randomized date – onset date of current depressive episode) / 7
- Total number of major depressive episodes in lifetime (excluding the current episode): 1, 2, 3-5, >5
- Overall severity of current episode (mild, moderate, severe, not reported)
- Overall severity of the first episode (mild, moderate, severe, not reported)
- Hospitalization events for current episode (Yes/No)
- Does the participant have any biological relatives who have or had diagnosis of Psychiatric disorder (yes, no)
- Current major depressive episode features
  - Anxious distress (yes/no)
  - Mixed features (yes/no)
  - Melancholic features (yes/no)
  - Atypical features (yes/no)
  - Catatonia (yes/no)
  - Seasonal pattern (yes/no)
- Number of failed antidepressant treatments prior to screening in current MDE (<3, >= 3).
- Reason for discontinuation of prior MDD related medication/therapies (due to lack of efficacy, adverse event, non-compliance, no longer required, others).

The antidepressant category of patients at baseline is summarized based on the actual baseline ADs collected in eCRF CM page, in the case that patient has no baseline antidepressant reported, the randomization strata from the IRT system will be used.

The baseline SoC category is summarized based on the number of ADs (monotherapy = only one AD; combinations = at least two ADs) and whether an augmentation therapy is used as combination therapy at baseline. The baseline SoC (AD or augmentation) is identified by CMCAT="MDD RELATED MEDICATIONS" in CM data and the ADs are selected by ATC3="ANTIDEPRESSANTS". The augmentation therapies are reported with CMCAT="MDD RELATED MEDICATIONS" in eCRF and confirmed during clinical review.

Demographic and other baseline data will be summarized descriptively by treatment arm for all study participants in the Randomized set.

### 2.3.3 Medical history and current medical condition

Any medical history and current medical conditions at baseline for all randomized patients will be coded using the Medical Dictionary for Regulatory Activities (MedDRA) and summarized by System Organ Class (SOC) and Preferred Term (PT) and by treatment arm.

All previous major depressive episodes (including current MDE) will be collected for each patient. For the reported first and current MDEs, the following criteria will be used to impute the partial start dates, which will be used in calculation of the disease duration and the duration of current episode defined in [Section 2.3.2](#).

- If year and month are present and day is missing (YYYY-MM-XX), impute the start date as YYYY-MM-15;
- If year is present and missing month and day (YYYY-XX-XX), use 01-July of that year (YYYY-07-01) as the start date.
- If completely missing, no imputation will be performed.

All collected information for MDEs will be listed at individual level and by treatment arms. No imputation is needed for the partial/missing start/end dates and the reported start/end dates will be used in the listing.

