2.2 Secondary estimands

Not applicable

3 Study design

Figure 3-1 Study Design

This is a non-confirmatory, randomized, double-blind, placebo-controlled, parallel-group trial in participants with TRD to evaluate the efficacy, safety, tolerability and pharmacokinetics of single subcutaneous MIJ821 administration in addition to pharmacological antidepressant SoC treatment. Approximately 56 participants will be randomized in a total of 20-25 centers worldwide.

Participants will be randomly allocated to one of the following four treatment arms in a 1:1:1:1 ratio:

- Single administration of MIJ821 s.c. 10 mg
- Single administration of MIJ821 s.c. 4 mg
- Single administration of MIJ821 s.c. 1 mg
- Single administration of Placebo s.c.

The screening period starts when the participant signs the informed consent form and can last up to 28 days. The eligibility of participants is determined based on the assessments performed during the screening period and also on Day 1, prior to randomization. With the exception of lab results, all other baseline evaluations including the primary efficacy scale (MADRS) must be performed on Day 1, prior to randomization, and reviewed against the eligibility criteria before dosing. On Day 1, eligible participants will then be randomized to one of the above treatment arms.

Treatment is administered as a single s.c. injection on Day 1, followed by a safety observation at the clinical site for a minimum of 4 hours after administration. Study participants will be continuously observed by site personnel during the first 30 minutes after administration for emergence of adverse events, particularly CNS or cardiovascular AEs. Safety assessments will

include physical examinations (PEs), ECGs, vital signs, standard clinical laboratory evaluations (hematology, blood chemistry, and urinalysis), administration of the CADSS, MOAA/S, C-SSRS, and memory assessment using orientation questions. Local tolerability will be evaluated by visual inspection of the injection area. Injection site abnormalities reaching the threshold of mild changes will also be assessed quantitatively (refer to Section 8.5.4).

Participants will be allowed to leave the clinical site at the earliest 4 hours after dosing, if all of the following criteria are fulfilled:

- The participant does neither report nor present with any CNS adverse events (dissociation, amnesia, sedation)

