5.1 Inclusion criteria

Participants eligible for inclusion in this study must meet all of the following criteria:

- 1. Signed informed consent must be obtained prior to participation in the study.
- 2. Male and female participants, 18 to 65 years of age (inclusive) at screening.
- 3. Participant has a diagnosis of recurrent MDD and a current major depressive episode of at least 8 weeks in duration as defined by DSM-5 criteria and confirmed by both the SCID-5 and an adequate clinical psychiatric evaluation at screening.
- 4. MADRS \geq 24 at screening and before randomization on Day 1.
- 5. Failure to respond to 2 or more antidepressant treatments but no more than 5, where the two failed treatments are two different antidepressants and at least one of which was used in the current depressive episode, with adequate dose and duration (≥ 6 weeks duration, doses defined per agent), as identified by the MGH-Antidepressant Treatment Response Questionnaire, based on the patient's report and prior psychiatric history, assessed by the investigator, and further documented by medical records. Patients with historical treatment failure to esketamine, ketamine or arketamine are excluded.
- 6. Participant must agree to receive pharmacological standard of care treatment to treat their MDD (as determined by the treating physician(s) based on clinical judgement and protocol recommendations) during the trial duration.
- 7. If the participant is taking any other type of psychotropic drugs, the dose of these drugs needs to be stable, where a stable dose of psychotropic drugs is defined as no changes in dose or type of e.g. antipsychotics or mood stabilizers for at least 6 weeks prior to baseline (if applicable).
- 8. The antidepressant should be at a stable dose for at least 4 weeks before baseline. No new antidepressant initiated 6 weeks or less before baseline. No psychotherapy initiated 4 weeks or less before baseline.
- 9. Able to communicate well, and to understand and comply with study requirements.

5.2 **Exclusion criteria**

Participants meeting any of the following criteria are not eligible for inclusion in this study:

- 1. Current acute depressive episode lasting longer than two years continuously, or participants receiving electroconvulsive therapy (ECT), transcranial magnetic stimulation (TMS), vagus nerve stimulation (VNS) or deep brain stimulation (DBS) in the current episode or within last year prior to screening (whichever is longer).

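### Imputing a year-only start of the current depressive episode as 1 July, with no bound at randomisation, can give an episode duration that is negative or outside the range the eligibility criteria allow

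*SAP*

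**What the plan says.** SAP 2.3.3 introduces its rule with "For the reported first and current MDEs, the following criteria will be used to impute the partial start dates". A start date with year and month takes the 15th. A start date with the year alone follows this line: "If year is present and missing month and day (YYYY-XX-XX), use 01-July of that year (YYYY-07-01) as the start date". A wholly missing date is left missing. The imputed dates feed both disease duration and current-episode duration; the listing keeps the dates as reported.

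SAP 2.3.2 gives the formula: "Duration of current depressive episode (weeks) derived as (randomized date – onset date of current depressive episode) / 7". It also derives disease duration, in years, from the date on which major depressive disorder was first diagnosed. On use, it says: "Demographic and other baseline data will be summarized descriptively by treatment arm for all study participants in the Randomized set".

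The protocol limits the current episode on both sides. Inclusion criterion 3 asks for "a current major depressive episode of at least 8 weeks in duration as defined by DSM-5 criteria", confirmed at screening. Exclusion criterion 1 (Protocol 5.2) rules out "Current acute depressive episode lasting longer than two years continuously". Protocol Section 3 adds the lag between the eligibility check and randomisation: "The screening period starts when the participant signs the informed consent form and can last up to 28 days".

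**The concern.** A mid-year default is neutral when the history is long and unbounded. The current episode is different: for an eligible participant its true length lies in a window of roughly two years that ends at least 8 weeks before screening. A fixed 1 July ignores both ends of that window and the randomisation date. It can therefore place the start of the episode after the participant was randomised, or so early that the participant appears to breach exclusion criterion 1.

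Episode duration is a standard descriptor of a treatment-resistant population. With 14 participants per arm, one impossible value would be the minimum or maximum in its column, and the summary would disagree with the listing, which shows the unimputed date.

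A second inconsistency sits beside it. SAP 2.3.3 sends imputed episode start dates into disease duration, while SAP 2.3.2 computes disease duration from the date of first diagnosis. An episode can begin before it is diagnosed, so two programmers could produce two different variables.

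**Working it through.** The plan states no figure here, so there is none to reproduce. The check is date arithmetic.

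**Inputs.** Imputed start: 1 July of the reported year (SAP 2.3.3). Duration = (randomisation date − start date) / 7 (SAP 2.3.2). True onset for an eligible participant: 56 days to 730 days before screening (Protocol 5.1 and 5.2). Screening to randomisation: 1 to 28 days (Protocol Section 3 and Table 8-1). The longest legitimate duration at randomisation is therefore 730 + 28 = 758 days, or 108.3 weeks. The example year 2023 is an assumption.

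**By onset year.**

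- *Same calendar year as randomisation.* The earliest feasible randomisation is 27 February (1 January + 56 days + 1 day). The imputed duration is negative for every randomisation from then to 30 June. From 1 July to 25 August it is 0 to 55 days, under 8 weeks.
- *Previous calendar year.* The imputed duration runs from 184 days (1 January) to 548 days (31 December), or 26.3 to 78.3 weeks. It is always in range.
- *Two calendar years back.* It runs from 549 to 913 days, or 78.4 to 130.4 weeks. It passes two years after 1 July and passes 758 days from 30 July.
- *Three calendar years back.* This is possible only for randomisation in January, because of the screening lag. It gives about 131 to 134 weeks, always out of range, but accounts for under 0.2% of cases.

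**Worked cases.**

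| Randomised | Reported year | Example true onset | True weeks | Imputed weeks |
|---|---|---|---|---|
| 27 Feb 2023 | 2023 | 1 Jan 2023 | 8.1 | -124/7 = -17.7 |
| 15 Mar 2023 | 2023 | 10 Jan 2023 | 9.1 | -108/7 = -15.4 |
| 15 Aug 2023 | 2023 | 1 Feb 2023 | 27.9 | 45/7 = 6.4 |
| 15 Nov 2023 | 2021 | 1 Dec 2021 | 102.0 | 867/7 = 123.9 |

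**How often, given a year-only date.** Every randomisation day in 2023 was paired with every eligible onset day, all weighted equally (an assumption). The upper limit is two years plus the lag.

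| Screening lag | Negative | 0 to <8 weeks | Above upper limit | Any |
|---|---|---|---|---|
| 1 day | 3.1% | 3.5% | 6.8% | 13.4% |
| 14 days | 2.5% | 3.2% | 6.8% | 12.5% |
| 28 days | 1.9% | 2.9% | 6.8% | 11.6% |

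**In the whole trial.** The share of dates that are year-only is not in the documents. If it were 5% to 20% of 56 participants (an assumption), that is 2.8 to 11.2 dates. At 12.5%, the expected number of impossible values is 0.35 to 1.4; at 2.5%, the expected number of negative values is 0.07 to 0.28.

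**Effect on an arm.** 1 July lies at most 183 days (26.1 weeks) from any day in its year. One such error moves a 14-person mean by at most 26.1/14 = 1.9 weeks. With durations uniform over 8 to 104 weeks, the SD is 96/√12 = 27.7 weeks and the standard error 27.7/√14 = 7.4 weeks.

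**The case against.** The strongest reply is that the failing cases are the ones least likely to be recorded by year alone. To enrol someone in March 2023 with onset in 2023, the site must know that the episode began in early January; to enrol someone in November 2023 with onset in 2021, it must know that it began late that year. That is close to month-level knowledge, and a date with a month takes the 15th instead. This stands as a reason to expect few cases, and the equal-weight calculation does not allow for it. It does not remove the gap: the SAP applies its year-only rule to the current episode, and Protocol 8.5.1.1 keeps the SCID-5 responses in source documents only, so what the site knew need not reach the database.

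A second reply is that the programming specification will deal with it. SAP 5.1 defers adverse-event and medication dates to that specification, but 2.3.3 does not defer: it states a complete rule without conditions.

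Several stronger readings are tempting and are not supported:

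- *The rule spoils year-only dates generally.* It does not. Onset in the previous calendar year, about 53% of the enumerated cases, is always in range.
- *It visibly distorts arm means.* A shift of at most 1.9 weeks is small against a standard error of about 7.4 weeks, and the median is reported too.
- *It makes eligible participants count as ineligible.* Protocol deviations are reported separately (SAP 2.3.1) and the listing shows the dates as reported.
- *It affects efficacy.* The ANCOVA in the protocol summary and the MMRM in SAP 2.6.1.1 do not include episode duration. Parts of the SAP, including the primary analysis, are blacked out, so this can be said only of the visible text.
- *Eligibility guarantees the 8-week to two-year range.* The table uses the Randomized set, and the SAP provides for protocol deviations and mistaken randomisation (5.5), so a genuine out-of-range value is possible.

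**Conclusion.** The point holds as a small defect in a stated rule. Followed exactly, SAP 2.3.3 can return a current-episode duration that is negative, shorter than 8 weeks, or longer than two years plus the 28-day screening lag, and no visible text corrects it. The individual date results need no assumption beyond the example year. The rate of about 12% to 13% rests on uniform onset and randomisation dates and is conditional on the date being year-only, which the documents do not quantify; the trial may see no case or one or two.

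The consequence is an implausible minimum or maximum in a descriptive baseline table. The eligibility limits, and therefore the out-of-range part of this point, do not apply to the first episode. The mismatch over the source date for disease duration is real and does not depend on how many dates are partial.

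**What to change.** For the current episode with a year-only start, replace 1 July by the midpoint of the part of the reported year that overlaps the interval from two years to 8 weeks before the participant's screening date. If there is no overlap, keep the 1 July default but never later than randomisation, and flag the record for eligibility or deviation review. The flag matters: forcing every date into the window would hide a true deviation.

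With an assumed 14-day screening lag, the change gives:

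- 15 March 2023, onset 2023: feasible 1 to 4 January, 10.3 weeks instead of -15.4.
- 15 August 2023, onset 2023: feasible 1 January to 6 June, 21.1 weeks instead of 6.4.
- 15 November 2023, onset 2021: feasible 1 November to 31 December, 102.0 weeks instead of 123.9.

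Separately, reconcile SAP 2.3.2 and 2.3.3 on disease duration by naming one source date, either first diagnosis or first-episode onset, and apply the partial-date rule to that date. If diagnosis is chosen, the rule must be extended, because it now covers only episode start dates.

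The cost is two or three sentences in the SAP, a small program change and one flag. No new data are needed.
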